15. DATA AND SAFETY MONITORING PLAN

A specific data and safety monitoring plan is only required for greater than minimal risk research. For guidance on creating this plan, please see the [Guidance Document](#) on the HRPP website.

Part I – this part should be completed for all studies that require a DSMP.

Part II – This part should be completed when your study needs a Data and Safety Monitoring Board or Committee (DSMB/C) as part of your Data and Safety Monitoring Plan.

Part I: Elements of the Data and Safety Monitoring Plan

- Indicate who will perform the data and safety monitoring for this study.*
- Justify your choice of monitor, in terms of assessed risk to the research subject's health and well being. In studies where the monitor is independent of the study staff, indicate the individual's credentials, relationship to the PI, and rationale for selection*
- List the specific items that will be monitored for safety (e.g. adverse events, protocol compliance, etc)*
- Indicate the frequency at which accumulated safety and data information (items listed in # above) will be reviewed by the monitor (s) or the DSMB/C.*

- *Where applicable, describe rules which will guide interruption or alteration of the study design.*
- *Where applicable, indicate dose selection procedures that will be used to minimize toxicity.*
- *Should a temporary or permanent suspension of your study occur, in addition to the IRB, indicate to whom will you report the occurrence.*

The Principal Investigator (PI) will be responsible for ensuring participants' safety on a daily basis, and that each individual engaged in research is qualified to do so by virtue of education, training and experience to perform the delegated task.

This project proposes a non-systematic collection method of reported events to determine if an adverse event has occurred, and to determine next steps, if any, for reporting. Events reported by participants that meet the definition of an adverse event during the time frame specified in the protocol (e.g., from the start of intervention through the end of study procedures) will be collected in electronic format using REDCap.

Definitions

Definitions are from the January 2007 OHRP Guidance on Reviewing and Reporting Unanticipated Problems Involving Risks to Subjects or Others and Adverse Events, OHRP Guidance.

Adverse Event (AE):

An unfavorable change in the health of a participant, including abnormal laboratory findings, that happens during a clinical study or within a certain amount of time after the study has ended. This change may or may not be caused by the intervention/treatment being studied. The Northwell Health IRB further defines AEs to encompass both physical and psychological harms.

Serious Adverse Event (SAE):

Any adverse event that:

- Results in death
- Is a life-threatening experience
- Hospitalization (for a person not already hospitalized)
- Prolongation of hospitalization (for a patient already hospitalized)
- Persistent or significant disability or incapacity
- Congenital anomaly and/or birth defects
- Event that jeopardizes the subject and may require medical or surgical treatment to prevent one of the preceding outcomes.

In this trial, we do not expect adverse events (serious or otherwise) to occur as part of care partner's participation in this research. We do not consider any patient-centered outcomes collected to require adverse event assessment.

Unanticipated Problem (UP):

Defined by DHHS 45 CFR part 46 as any incident, experience, or outcome that **meets all the following criteria:**

- unexpected, in terms of nature, severity, or frequency, given (a) the research procedures that are described in the protocol-related

- documents, such as the IRB-approved research protocol and informed consent document; and (b) the characteristics of the study population;
- related or possibly related to participation in the research (in this guidance document, possibly related means there is a reasonable possibility that the incident, experience, or outcome may have been caused by the procedures involved in the research);
 - suggests that the research places participants or others at a greater risk of harm (including physical, psychological, economic, or social harm) than was previously known or recognized.

CLASSIFYING ADVERSE EVENTS

Should adverse events be reported, the severity, expectedness, and potential relatedness to the study intervention will be classified according to the below:

Severity

- **Mild:** Awareness of signs or symptoms, but easily tolerated and are of minor irritant type causing no loss of time from normal activities. Symptoms do not require therapy or a medical evaluation; signs and symptoms are transient.
- **Moderate:** Events introduce a low level of inconvenience or concern to the participant and may interfere with daily activities but are usually improved by simple therapeutic measures; moderate experiences may cause some interference with functioning.
- **Severe:** Events interrupt the participant's normal daily activities and generally, require systemic drug therapy or other treatment; they are usually incapacitating

Expectedness

AEs will be assessed as to whether they were expected to occur or unexpected, meaning not anticipated based on current knowledge found in the protocol.

Categories are:

- **Unexpected** - nature or severity of the event is not consistent with information about the condition under study or intervention in the protocol, consent form, product brochure, or investigator brochure.
- **Expected** - event is known to be associated with the intervention or condition under study.

Relatedness

The event's potential relationship to the study intervention and/or participation is assessed according to the below:

- **Related:** An event is "related" if it is likely to have been caused by the research procedures.

- **Probably/Possibly Related:** An event is considered to be probably or possibly related to the intervention if there is a greater than 50% chance that the event was caused by the study procedures.
- **Unrelated:** The adverse event is clearly not related to the research - i.e., another cause of the event is most plausible; and/or a clinically plausible temporal sequence is inconsistent with the onset of the event and the study intervention and/or a causal relationship is considered biologically implausible.

REPORTING PROCESSES

All **adverse events that are serious** (SAE), **unexpected** (have not been defined as expected) and **related** to the research will be reported to the NIA Program Officer, the study's Data and Safety Monitoring Board (DSMB) chair, and the Northwell Health IRB within **48 hours** of the study's knowledge of the SAE, per NIA policy.

Unanticipated Problems (UP) that are determined by the Northwell Health IRB to meet the criteria of an Unanticipated Problem as defined above by will be reported to the NIA Program Officer and the study's Data and Safety Monitoring Board (DSMB) within **48 hours** of that determination. A report will be submitted to OHRP by the Northwell Health IRB as per 45 CFR 46(a)(4)(i), and according to the IRB's standard operating procedures for reportable events.

All other adverse events (events that meet the definition of an AE, but are not unanticipated problems or an unexpected, related SAE) will be reported to the study's DSMB **annually**, or at a frequency requested by NIA Program Officer and/or by the DSMB.

|

Part II: Data and Safety Monitoring Board or Committee

- *When appropriate, attach a description of the DSMB.*
- *Provide the number of members and area of professional expertise.*
- *Provide confirmation that the members of the board are all independent of the study.*

Although this single-site study is considered minimal risk, the funding agency (NIA) has appointed a data safety and monitoring board. Please see the attached DSMB Charter for more information. The NIA-appointed DSMB will provide recommendations for study initiation to the study team and NIA electronically, via email, prior to the start of the research. Meetings of the DSMB will then be held regularly (e.g., every six to nine months) at the call of NIA or the DSMB Chair.

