We will randomize (blind allocation) the care partner to either the enhanced condition (usual care, including speech language pathologist (SLP) contact information) or the intervention (usual care, including SLP contact information, + WeCareToFeedDysphagia). The study team will collect in the Time Point 1 measures, sociodemographic information, caregiving measures, as well as baseline

ZBI-22, CarerQol, CARES Part A and Part B, EdFED-Q, and QUALID via REDCap. In addition, the study team will collect relevant clinical data from the patient record (see Section 14 for a full list of variables collected via EHR and care partner survey).

Enhanced Control Condition (n=40)

In the enhanced control condition, following completion of baseline measures, the care partner will continue to receive usual care from the patient's medical team. The study team will provide information regarding contacting a speech language pathologist for further information regarding caring for someone with AD/ABRD and OD. The care partners will also receive information regarding contact for remaining study assessments (1 month and 3 months post-discharge).

Intervention Condition (N=40)

In the intervention condition, following completion of baseline measures, the care partner will continue to receive usual care from the patient's medical team, plus the study team will provide access to WeCareToFeedDysphagia. The study team will provide all participants a copy of the information sheet, the team's contact information, and a reminder that study personnel will contact them by phone 1 week post-discharge to assess tool use and answer any questions. The study team will provide unique

usernames and passwords to participants in the intervention condition and instructions on how to access WeCareToFeedDysphagia from any smart device (e.g., smartphone) or computer. Care partners will receive a text message reminder about the WeCareToFeedDysphagia resource 1 week, 2 weeks, and 3 weeks after initial access is granted to the care giver.

Participants in both the enhanced control condition and the intervention condition will receive text message link to complete repeat assessments of the ZBI-22, CarerQol, CARES Part A and Part B, EdFED-Q, and QUALID one month post-hospital discharge (Time Point 2) and 3 months post-hospital discharge (Time Point 3) via REDCap. For those care partners who are unable to complete the REDCap survey on their own, a member of the study team will set up a 30-minute

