17. RISKS TO SUBJECTS

- *Describe any potential risks and discomforts to the subject (physical, psychological, social, legal, or other) and assess their likelihood and seriousness and whether side effects are reversible. Where appropriate, describe alternative treatments and procedures that might be advantageous to the subjects.*
- *Include risks to others , like sexual partners (if appropriate)*
- *Discuss why the risks to subjects are reasonable in relation to the anticipated benefits and in relation to the importance of the knowledge that may reasonably be expected to results*
- *Describe the procedures for protecting against or minimizing any potential risks, including risks to confidentiality, and assess their likely effectiveness.*

The probability and magnitude of harm or discomfort anticipated from the care partner's participation in this research is not greater than those ordinarily encountered in daily life.

Potential risks associated with the intervention include:

- *Psychological risks:* Some of the assessment questions may be considered personal or may be upsetting to participants; such experiences are usually temporary. We will inform individuals they can skip any question they do not want to answer during the interview process and will provide linkage to care (counseling) should a care partner become distressed or uncomfortable during the interviews. In the event of high levels of distress, the participant will be referred to our NWH outpatient geriatrics faculty practice or our adult outpatient psychiatry service. The study team will facilitate this connection for all interested study participants. They may alternately be referred to the Alzheimer's Disease Caregiver Support Initiative and/or provided information on Alzheimer's Disease and Healthy Aging, Caregiving Support by the Centers for Disease Control and Prevention (CDC). Resources and support.
- *Privacy risks:* A potential risk of taking part in this study is the possibility of a loss of confidentiality or privacy. Measures to mitigate risks to loss of privacy are detailed in Section 20.

The study team will explain to participants that participation is voluntary and they are able to withdraw at any time without impacting the current or future care of the care partner or the patient at Northwell Health.

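### Adverse events are recorded only if volunteered, the collection window is never fixed and its one example starts after the baseline questionnaire, and scheduled staff contact may differ by arm

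*Combined protocol and SAP*

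**What the plan says.** - **Method (Section 15, Part I).** "This project proposes a non-systematic collection method of reported events to determine if an adverse event has occurred". The events in question are those that participants report; no one is told to ask.
- **Window (same paragraph).** Events are collected "during the time frame specified in the protocol (e.g., from the start of intervention through the end of study procedures". No other section sets a time frame.
- **Definition (Section 15, Definitions).** An adverse event is an unfavorable change in a participant's health "that happens during a clinical study or within a certain amount of time after the study has ended". The paragraph ends: "The Northwell Health IRB further defines AEs to encompass both physical and psychological harms".
- **Named risk (Section 17).** "Some of the assessment questions may be considered personal or may be upsetting to participants".
- **Sequence (Section 11).** Both arms complete baseline measures first. Intervention participants then receive the tool. Controls receive usual care and speech language pathologist contact details, and are offered the tool only after Time Point 3.
- **1-week call (Section 11, Intervention Condition).** Participants are reminded that "study personnel will contact them by phone 1 week post-discharge to assess tool use and answer any questions". The control paragraph says only: "The care partners will also receive information regarding contact for remaining study assessments (1 month and 3 months post-discharge".
- **Measures (Sections 11 and 14).** The questionnaires, chart data and patient outcomes listed include no adverse event question.

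**The concern.** Two separate things look wrong.

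The first is coverage. The psychological risk that the protocol names arises from answering the questionnaires, and these are first answered at Time Point 1. A window that opens with the intervention opens too late to include that occasion. For controls it is unclear what would open it.

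The second is ascertainment. When nobody asks, the number of events recorded depends on how often a participant happens to be in touch with staff. If one arm has a scheduled live call and the other does not, the same true event may have a different chance of being recorded in each arm.

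At stake is how the safety record of this pilot is read by the monitoring board, and by those planning the full-scale trial. Few or no volunteered reports would say little, and a small difference between arms could reflect contact alone.

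**Working it through.** The plan gives no adverse event rate, hypothesis or between-arm test, so there is no stated figure to reproduce. The check compares the text and then illustrates the possible size.

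**1. Does baseline distress fall inside the window?** By the Section 15 definition, yes: it is a psychological harm that happens during the study. By the example window, no: Section 11 places tool access after completion of the baseline measures. The definition and the example within Section 15 do not match, and the example omits the first occasion of the risk named in Section 17.

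**2. Would staff notice distress anyway?** Section 17 offers linkage to counseling for distress during interviews. By default, though, the assessments are self-completed through a REDCap link. A video call is used at baseline only if the care partner prefers it, and later only if the care partner cannot complete the survey alone.

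**3. Scheduled post-baseline contacts named in Section 11.**

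| | Control | Intervention |
|---|---|---|
| Survey links (1 and 3 months) | 2 | 2 |
| Text reminders (weeks 1, 2, 3) | 0 | 3 |
| Staff call (1 week) | 0 | 1 |
| Total | 2 | 6 |

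The optional video help with surveys is open to both arms and is not counted. The zero for the control call is an inference. The sentence that mentions the call sits under the intervention heading but speaks of all participants, and the text-receipt criterion in Sections 10 and 12 ties the call to care partners without naming an arm. Two things favor the intervention-only reading: the call is meant to assess tool use, and the tool-access criteria in the same lists also say care partners although only one arm has access before Time Point 3.

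**4. Illustration if the call is intervention-only.** Input from Section 12: n = 40 per arm. Assumptions, none of them in the documents: true event rate p = 5–20%, equal in both arms; volunteered reporting s = 30–50%; share of otherwise unreported events picked up by a call c = 0–30%.

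- Control expected count = n·p·s
- Intervention expected count = n·p·[1 − (1 − s)(1 − c)]
- Ratio = [1 − (1 − s)(1 − c)] / s (p cancels)

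| s | c | 1 − (1 − s)(1 − c) | Ratio |
|---|---|---|---|
| 0.3 | 0 | 0.30 | 1.00 |
| 0.5 | 0.1 | 1 − 0.5 × 0.9 = 0.55 | 1.10 |
| 0.3 | 0.1 | 1 − 0.7 × 0.9 = 0.37 | 1.23 |
| 0.5 | 0.3 | 1 − 0.5 × 0.7 = 0.65 | 1.30 |
| 0.3 | 0.3 | 1 − 0.7 × 0.7 = 0.51 | 1.70 |

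The smallest non-zero excess is 40 × 0.05 × (0.55 − 0.50) = 0.10 events. The largest is 40 × 0.20 × (0.51 − 0.30) = 1.68 (4.08 against 2.40). If the call elicits nothing, or both arms receive it, the ratio is 1.00. The model lets a call only add reports, so its direction is assumed and not found.

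**5. Baseline distress left out.** At an assumed 2–10%, the omission is 40 × 0.02 = 0.8 to 40 × 0.10 = 4.0 events per arm, or 1.6 to 8.0 in total. Both arms answer the same measures before any intervention, so the expected between-arm difference is 0. One caveat: Section 12 has the coordinator request the allocation before each consent, so staff may know the arm at baseline. Nothing in the documents shows that this would change what is recorded.

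**The case against.** Passive collection is an openly declared choice in a minimal-risk pilot. The template text in Section 15 requires a specific monitoring plan only for greater-than-minimal-risk research, and a funder-appointed board is nevertheless in place. Participants may skip questions, and counseling is offered whatever the adverse event window. This stands, and it limits the urgency. It does not reconcile the definition, the example window and the named risk.

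A reader might go further in four ways that the documents do not support.

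- *That baseline distress is excluded outright.* The window is introduced as an example, and the definition is broader. The sound finding is that the window is never fixed.
- *That adverse event counts by arm are biased.* The call's scope is ambiguous, its stated purpose is not to elicit events, and neither Section 10 nor Section 12 makes adverse events an endpoint or plans a comparison. The counts may be affected; that is all that can be said.
- *That the missing baseline events cause such a bias.* They would under-count both arms alike.
- *That the monitoring board could not see harm from the tool.* Burden, caregiver stress and quality of life are measured on the same schedule in both arms, as are acute care visits, dehydration, weight loss and behavioral symptoms in the patients. Section 15 keeps the patient outcomes out of adverse event assessment, but they are still collected.

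**Conclusion.** The point holds in a limited form. Section 15 relies on volunteered reports and gives only an example window. That example begins after the baseline questionnaire and has no clear start for controls, which does not fit the protocol's own definition or its named risk. This part rests on the text alone.

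The unequal chance to report rests on reading the 1-week call as intervention-only, which is the most natural reading but not a certain one. Its size and direction cannot be computed from the documents. The range of 1.00 to 1.70, or 0 to 1.68 extra events among 40, rests wholly on the assumed rates. Severity is modest, since the study is minimal-risk and adverse events are not an endpoint. The change is still worth making because it is cheap and the pilot is meant to inform a larger trial.

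**What to change.** 1. In Section 15, replace the example with one window for both arms, from consent through completion of Time Point 3.
2. Add the same short care-partner adverse event and distress question to the REDCap surveys at baseline, 1 month and 3 months in both arms, with an alert to the study team. At baseline, place it after the other measures so that it can capture distress they cause. List it in Section 14.
3. Record the source of each report (survey, call, spontaneous), and base any by-arm summary on survey-elicited events, with the number of survey completers as denominator.
4. In Section 11, state which arm or arms receive the 1-week call.

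Keep the question to the care partner. Extending it to the patient would first have to be reconciled with the Section 15 statement that patient-centered outcomes do not require adverse event assessment.

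The cost is one added question in three surveys that both arms already complete, plus wording changes in Sections 11, 14 and 15. The downside is more unrelated minor events to log and classify.

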virtual (Microsoft Teams or Zoom) call to facilitate completion of the outcome assessments.

The study team will also collect patient-centered outcomes (defined in Section 14 below) at 1-month and 3-months post initial hospital discharge.

After care partners complete their Time Point 3 assessment, we will offer all care partners access to WeCareToFeedDysphagia. |

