Caregiving measures will consist of the relationship between care partner and patient; time since assuming the care partner role; number of other care partners; overall number of caregiving responsibilities (e.g., financial, physical, medical); OD-related caregiving responsibilities (e.g., purchasing and preparing food, feeding); and other factors of caregiver burden such as clinical and psychiatric comorbidities.

Patient-Centered Outcomes

Patients will be assessed for outcomes including 1) acute care visits (emergency department visits and hospital readmissions; differentiating between aspiration and non-aspiration related complaints); 2) dehydration (requiring intravenous or subcutaneous fluid administration); 3) nutritional intake (weight loss greater than 3 kg, 1-3 kg, and no weight loss; derived from the Mini Nutritional Assessment, MNA); 4) behavioral and psychological symptoms of dementia (BPSD, Neuropsychiatric Inventory Questionnaire, NPI-Q).

National Institutes on Aging Clinical Research Operations & Management System (CROMS) Screening and Enrollment Questionnaires

The funding agency of this study requires the collection of standardized demographic information from all funded clinical trial aims and enrollment to facilitate early interventions to help with enrollment challenges, particularly among underrepresented populations. Participants will have the ability to select "prefer not to answer" to any of the items listed. Variables collected include age, sex, gender, sexual orientation, race, ethnicity, patient's cognitive status, education level, household income, occupation category, marital status, living situation, primary language spoken, insurance status, zip code, and dates associated with screening, enrollment, and study participation

All data collected for this research will be maintained in its original and unaltered source data state indefinitely and stored within the Quantitative Intelligence Data

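### Section 15 exempts the collected patient outcomes from adverse-event assessment and defines 'possibly related' in two conflicting ways, so it commits to no systematic interim review of patient harm

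*Combined protocol and SAP*

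**What the plan says.** **The exemption.** Section 15 says that no adverse events are expected from the care partner's participation and then adds: "We do not consider any patient-centered outcomes collected to require adverse event assessment". It gives no reason for the second statement.

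**What is exempted.** Section 14 lists the patient-centered outcomes. The first is "acute care visits (emergency department visits and hospital readmissions; differentiating between aspiration and non-aspiration related complaints", and the second is "dehydration (requiring intravenous or subcutaneous fluid administration". Weight loss and behavioral symptoms complete the list. On timing, Section 11 says: "The study team will also collect patient-centered outcomes (defined in Section 14 below) at 1-month and 3-months post initial hospital discharge".

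**The definitions.** Section 15 defines an AE as an unfavorable change in a participant's health, whatever its cause. Its SAE criteria include death and "Hospitalization (for a person not already hospitalized". Section 23 calls patients secondary participants and has the care partner give surrogate consent for them.

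**Relatedness.** In the definition of an unanticipated problem (UP), "possibly related means there is a reasonable possibility that the incident, experience, or outcome may have been caused by the procedures". In the AE classification, an event is probably or possibly related "if there is a greater than 50% chance that the event was caused by the study procedures".

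**Reporting.** SAEs that are both unexpected and related are reported within 48 hours. UPs are reported within 48 hours of the IRB's determination. All other AEs go to the DSMB once a year, or as often as NIA or the DSMB asks. On the board's schedule: "Meetings of the DSMB will then be held regularly (e.g., every six to nine months". AEs are collected by a non-systematic method.

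**The concern.** The tool advises care partners on dysphagia diets, feeding goals and management skills for patients who have trouble swallowing. If the guidance did harm, it would most plausibly show in the patient as aspiration, dehydration or readmission. Section 3 names aspiration, malnutrition and mortality as outcomes of dysphagia in these patients, and choking and dehydration as problems that care partners must manage. The trial collects several of these outcomes, but the safety plan sets them aside.

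At stake is whether the DSMB can see, while the trial runs, whether such events are more frequent in the intervention arm. Two people applying the section's relatedness wording to the same event could also classify it differently.

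**Working it through.** The plan gives no figure to reproduce on this point. The check is a comparison of texts, followed by simple timing arithmetic.

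**1. Does a collected outcome meet the SAE definition?** The patient is a secondary participant (Section 23). A readmission after discharge is an unfavorable health change in a person not already in hospital, and cause is irrelevant to the AE definition. A readmission therefore fits the SAE wording, and the exemption removes it. Both statements are in Section 15 and they cannot both be applied.

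**2. How would a minority-probability event be classified?** Take, for illustration, an event judged 20% to 50% likely to have been caused by the tool.
- Under the UP wording it can be possibly related, because a reasonable possibility is enough.
- Under the AE scale it is not, because the threshold is above 50%. It would usually be recorded as 'Unrelated', since that class includes events for which a different cause is the likeliest explanation.

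**3. Which routes to the DSMB remain for an aspiration-related readmission?**

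| Route | Requirement | Obstacle |
|---|---|---|
| 48-hour SAE | Serious, unexpected and related | Exempt from assessment; events linked to the condition count as expected; unclear whether 'related' includes 'Probably/Possibly Related' |
| 48-hour UP | IRB finds it unexpected, possibly related and suggestive of greater risk | Must be raised ad hoc; unexpected frequency qualifies, but Section 15 assigns nobody to produce by-arm counts |
| All other AEs, annual or on request | Meets the AE definition; relatedness irrelevant | Exempted outcomes have no stated path into this route |

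The expectedness filter works independently of relatedness. Correcting the 50% threshold alone would still leave most aspiration events outside the 48-hour SAE route.

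**4. Timing.** Inputs are N = 80 (Section 8), 3 months of follow-up (Section 9), and enrollment over A = 12 months (Section 9) or A = 6 months (Section 12). I assume uniform accrual, follow-up counted from enrollment, no attrition, and DSMB meetings and a first annual report timed from the start of enrollment. The number with follow-up finished at month t is 80 × (t − 3)/A, capped at 80.

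| Month | A = 6 | A = 12 |
|---|---|---|
| 6 | 80 × 3/6 = 40 | 80 × 3/12 = 20 |
| 9 | 80 × 6/6 = 80 | 80 × 6/12 = 40 |
| 12 | 80 (cap) | 80 × 9/12 = 60 |

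A DSMB meeting at 6 to 9 months would have complete data on 20 to 80 of the 80. By a first annual report at month 12, 60 to 80 would have finished.

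**The case against.** The sponsor can fairly say that the study is described as minimal risk, that usual care continues in both arms, and that the template requires a monitoring plan only above minimal risk. In a population where aspiration and readmission are common, exempting them from event-by-event assessment is partly a legitimate design choice. This supports limiting individual expedited reports. It does not explain why the appointed DSMB should have no scheduled view of the totals.

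Several stronger readings are tempting, and the documents do not support them:

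- **That patient harm would never reach the DSMB.** The UP route uses the lower threshold and covers harm to participants or others. NIA or the DSMB may ask for more frequent reports. The DSMB Charter, cited as attached but not available here, may provide for review of patient outcomes.
- **That the 50% wording blocks reporting.** It affects the 48-hour SAE route. The residual route takes AEs whatever their relatedness.
- **That every event at or below 50% has no category.** Most would fall under 'Unrelated'. Only events without a leading alternative cause are left unclassified.
- **That the full-scale trial would start with no safety comparison.** Section 12 lists patient-centered outcomes as exploratory and plans descriptive summaries by condition. The gap is in interim review. None of the six go/no-go criteria uses these outcomes, however.
- **That death is exempted.** It is not among the Section 14 patient-centered outcomes, so the exemption does not reach it. The weakness is different: Section 12 anticipates attrition from patient mortality, but nothing commits the team to recording deaths systematically.

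**Conclusion.** The point holds as a conflict within Section 15 and a gap in interim oversight. The exemption contradicts the protocol's own AE and SAE definitions as applied to secondary participants. 'Possibly related' has two incompatible meanings. The 48-hour SAE rule is ambiguous on relatedness and, through expectedness, would leave out most aspiration events in any case. Section 15 commits to no systematic interim review of patient harm.

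The exemption applies to all collected patient-centered outcomes in the patients of all 80 care partners. The documents give no event rates, so the number of events affected cannot be estimated. The timing range of 20 to 80 patients with complete data at a 6-to-9-month meeting rests on the accrual assumptions stated above. The conclusion on interim review would change if the DSMB Charter already schedules by-arm patient outcomes. The conflicts in definition would remain. This should be corrected, but it does not affect the sample size or the primary effect-size analysis.

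**What to change.** 1. Reconcile the exemption in Section 15 with the AE and SAE definitions. Either remove it, or limit it to individual expedited reporting and give the reason.
2. Give the DSMB, at each meeting, a descriptive by-arm table of aspiration-related acute visits, other acute visits and dehydration, taken from the existing 1- and 3-month collection. Add patient deaths, recorded as a reason for non-completion.
3. Use one definition of 'possibly related' throughout, namely the protocol's own UP wording, and state that the 48-hour SAE rule covers both related and possibly related events.
4. State how 'expected' applies to events linked to the condition, with excess frequency judged from the by-arm table.
5. If the Charter already provides for this review, cross-refer to it in Section 15.

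The cost is protocol wording and one short table per meeting, mostly from data already collected. Deaths need one added reason code. A few more events will have to be classified. By-arm counts in 80 patients are descriptive only: they can prompt a question but cannot establish or exclude harm.
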